## 4. SELECTION AND ENROLLMENT OF PARTICIPANTS

#### 4.1 Inclusion Criteria

All subjects must meet the inclusion criteria below to participate in this study. Any waiver of these inclusion criteria (or the subsequent exclusion criteria) must be approved by the Clinical Director on a case-by-case basis prior to enrolling the subject, and documented in the subject's Case Report Form (TR-1131-FORM-10).

- Predominant stress urinary incontinence as determined by responses to a series of three standard questions from the King's Health Questionnaire; specifically:
  - An affirmative response to "Do you lose urine with physical activities such as coughing, sneezing, running?",

- An affirmative or negative response to "Is it very difficult to control when you have a strong urge to urinate?",
- And, if an affirmative response to the second question, a negative response to "Are more of your incontinence episodes due to a strong urge to urinate than to abdominal pressure such as sneezing?"
- Mild-moderate incontinence symptoms as determined by self-reported typical number of accidents of 1 per 24 hours or more. Symptom severity is later verified with data from the Daily Log (See 5.4)
- Age: 21-75y
- Gender: Female

## 4.2 Exclusion Criteria

Subjects will be excluded from enrollment if they meet any of the following criteria:

- Severe incontinence as determined by self-reported >5 accidents in 24-hr period
- Currently pregnant, may be pregnant, attempting to become pregnant, or delivery within previous 6 weeks
- Implanted cardiac device, untreated cardiac arrhythmia or suffer from other heart problems.
- Cancer, epilepsy or cognitive dysfunction
- Vaginal or pelvic surgery within previous 6 months
- Complete denervation of the pelvic floor
- History or symptoms of urinary retention, extra-urethral incontinence, overflow incontinence
- Active urinary tract infection (UTI) or history of recurrent UTIs (more than three in a year)
- Recurrent vaginitis (bacterial/fungal)
- Pelvic pain/painful bladder syndrome
- Underlying neurologic/neuromuscular disorder
- Severe Obesity as defined by BMI >= 35
- Chronic coughing
- Impaired decision making, drug or alcohol dependence, or suicidal thoughts.
- Anyone who lacks the capacity to consent for themselves or who requires a legal representative to give informed consent.

## 4.3 Study Enrollment Procedures

The study uses the following multi-step process to achieve enrollment:

## Recruitment

- Ads placed in social media and other forums will attract candidates to a website that describes the study.
- Ads will be placed in the US without geographic targeting.
- Ads will be served to candidates using keywords (e.g. "incontinence").
- Alternately, healthcare providers who become familiar with the study can direct candidates to the study. These candidates will go through the same screening as all candidates and the referring healthcare provider would not be considered a study investigator. It is permissible for the referring healthcare provider to assist the candidates with completion of screening/consent information and to forward the information directly to Elidah.
- TR-1131-FORM-14 identifies the language that will be used in recruitment messaging.

## Screening

- Interested candidates complete an online survey comprising Screening Questions (TR-1131-FORM-13)
- Responses are maintained electronically in a Screening Log (TR-1131-FORM-11) which includes candidate contact information, date of survey completion, and survey responses.
- Survey responses will be reviewed to confirm that (based on IP addresses and/or provided contact info) candidates did not complete the survey multiple times with different responses, potentially in an attempt to qualify for enrollment.
- Hardcopy or verbal responses are acceptable and will be manually entered into the Screening Log.

## Consent

- Candidates that meet the enrollment criteria based on responses to the screening survey are contacted by Elidah.
- Study personnel describe the study requirements, respond to any questions from the candidate and explain the consent process (see 11.2). Notes of this communication are maintained in the Case Report Form (TR-1131-FORM-10) if enrolled, or in the screening log if not enrolled.
- Consent documentation (TR-1131-FORM-5) is sent to the candidate either electronically or as a hardcopy.
- The candidate returns the signed consent form, or via an online option.
- The candidate is now considered a "subject", and a sequential Subject Number is assigned (TR-1131-FORM-7).
- A copy of the signed consent document is maintained in the subject's Case Report File.

## **Treatment Initiation**

- Study materials are sent to the subject for treatment initiation (see 10.1 and 10.2)
- Confirmation of eligibility is based on baseline data per 5.4.

## 4.4 Recruitment Strategies

Appreciating that achieving enrollment targets in a clinical study can be challenged by various factors, including difficulty in identifying qualified candidates and candidates not wanting to participate in a study in which they may be assigned to a control group, Elidah has implemented several strategies to mitigate such challenges including:

- Recruitment using social media allows access to thousands of women from across the US, which additionally encouraging participation from a diverse pool of candidates.
- The active to control enrollment ratio is 2:1, giving subjects a greater chance of being assigned to a group that will realize a clinical benefit.
- Subjects in the control arm will optionally be allowed to pursue 6 weeks of treatment with the active device after completion of the control study requirements. Although the subject may elect to monitor and report her experience with the active device, such data will not be included in the analysis of the primary endpoint.

## 4.5 Retention Strategies

- Subjects who complete the study will be paid \$200 in cash or equivalent gift card. If the subject does not complete all study requirements the Clinical Director has discretion to compensate with a lesser amount.
- Subjects will be contacted after the 1st, 6th and 12th weeks to confirm ongoing participation and to provide the opportunity for subjects to ask questions.
- Subjects will have the option to download a mobile app that can keep track of progress of intensity level, days used, and leaks (if they enter it). This would not replace the diary.

## 5. STUDY DESIGN & PROCEDURES

## 5.1 Study Type

Randomized, controlled, prospective clinical study. Subjects will be assigned to the arms (i.e. treatment and control groups) in a 2:1 ratio.

### 5.2 Number of Subjects

An analysis of statistical power determined that 40 subjects in the active group and 20 subjects in the control group is likely sufficient to achieve statistical significance with respect to the primary outcome measure. Appreciating that some subjects who are initially enrolled will fail to complete treatment and return the study materials, it is likely that 70-80 subjects will be enrolled. See 9.1 for discussion of the sample size calculation.

### 5.3 Description of Evaluations

This research utilizes validated methods for evaluating the clinical impact of the device/treatment, including several identified in the FDA guidance document regarding clinical studies that investigate urinary incontinence. Stress urinary incontinence episodes per day data, obtained from the subject's Daily Log, serves as the primary efficacy outcome measure (see 2.2). Analysis of adverse events serves as the primary safety outcome measure (see 2.2). Evaluations utilized throughout the study are described below. See 9.5 for detail regarding strategies for analyzing the data obtained in these evaluations.

- I-QoL Questionnaire (Pre- and Post-study) the Incontinence Quality of Life (I-QoL) questionnaire is validated tool for assessing changes in the degree to which urinary incontinence affects a woman's quality of life (TR-1131-FORM-2). It comprises 22 questions, to which the subject provides a numeric response on a 1-5 scale. The score is the sum of the numeric responses, which can range from 22 to 110. A change of 2.5 points is considered clinically significant. The I-QoL questionnaire is provided to the subjects as part of pre- and post-study materials. Completed questionnaires are returned to Elidah via mail or electronically (see 10.4).
- 24-Hour Pad Weight Test (Pre- and Post-study) This test is used to quantify the volume of urine leakage. The subject wears an absorbent pad(s) over a period of 24 hours, after which the pad(s) are weighed to determine the mass of any leaked urine. A reduction of ≥50% compared to a baseline measure is considered clinically significant. A mass of less than 1.3g is considered to be "dry", i.e. no leakage. Pre-weighed pads will be sent to the subjects as part of the study materials. During pre- and post-study assessments the subjects will wear the pad(s) for 24 hours, seal the pad(s) in a moisture proof bag, and mail to Elidah for weighing. Note that although this assessment does provide an objective

measure of change in leakage volume, the method is known to be subject to variability, may not be meaningful to patients, and requires subject compliance. For this reason, Elidah has identified this tool as a secondary outcome measure and does not intend to use the data as a primary means for establishing device efficacy.

- **Pre-Study Incontinence History and Usability Questionnaire** (Pre-study) Included in the pre-study activity is a questionnaire that investigates each subject's medical history as it pertains to incontinence as well as their perceptions and preferences regarding incontinence treatments (TR-1131-FORM-1). Some of this information may be utilized in post hoc subgroup analysis (see 9.5). It may also be useful in informing strategies for Elidah to effectively reach potential patients.
- Daily Log (Baseline week and treatment weeks) Subjects are required to maintain a Daily Log throughout the study (i.e. baseline week through 12th week). Among other items they log their treatment completion (Y/N), treatment intensity (0-35), number of incontinence episodes, and number of pads used (TR-1131-FORM-3). The log also provides space for the subject to add notes that may be relevant to subsequent analysis. The log is maintained by the patient in hardcopy and returned to Elidah at the end of the study for analysis (see 10.4). Alternatively, an equivalent electronic form may be utilized. The stress urinary incontinence episodes per day data will serve as the primary outcome measure (see 9.5). See 9.5 regarding handling of missing information, particularly as it relates to the weeks between the baseline and 12th week.
- **Post-Study Usability Questionnaire** (Post-study) At the end of the study subjects are asked for feedback regarding any perceived improvement in continence, their satisfaction with the treatment, the ease of use, and other issues that may inform opportunities for future device/treatment improvements (TR-1131-FORM-4).
- Adverse Events (Throughout Study) See 7.3.

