#### 2.2 Primary Endpoint

Treatment efficacy is assessed by comparing the average number of stress urinary incontinence episodes per day at the end of treatment to the corresponding pre-treatment number.

Safety is determined by review of Adverse Events as defined in 7.3, and determination of no serious adverse event during the study.

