### 7.3 Adverse Events and Serious Adverse Events

Adverse events are the primary means for assessing device/treatment safety. Adverse events may be identified through direct communication with the subjects and through analysis of study materials.

For all adverse events, sufficient information will be pursued and/or obtained so as to permit (1) an adequate determination of the outcome of the events (i.e., whether the effect should be classified as a serious adverse effect) and (2) an assessment of the casual relationship between the adverse event and the device/treatment.

Adverse events determined to be associated with the device/treatment will be followed until they are resolved or stabilized. The CTCAE definitions and scoring of Adverse Events will be used.

An **adverse event (AE)** is generally defined as any unfavorable and unintended symptom or finding which either occurs during the study, having been absent at baseline, or, if present at baseline, appears to worsen during the study. Adverse events are recorded regardless of their relationship to the study intervention.

A **serious adverse event (SAE)** is generally defined as any adverse event that results in death, is life threatening, requires inpatient hospitalization or prolongation of existing hospitalization, results in persistent or significant disability/incapacity, or is a congenital anomaly: Grades 3-5.

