## 7.4 Reporting Procedures

Subjects are instructed to report adverse events at the time of occurrence via either phone or email. Adverse events may also be identified during routine communication with the subject (e.g. 6th week follow-up) or review of the subject's Daily Log.

The Data Safety and Monitoring Board will use the following 0 to 5 scale to grade adverse events (AE): 0 = none or event is not clinically significant, 1 = mild AE that does not require treatment, 2 = moderate AE that does require treatment, but resolves completely, 3 = severe AE (e.g. one that results in temporary inability to conduct one or more everyday activities and requires ongoing medical attention), 4 = life threatening or results in permanent inability to conduct one or more everyday activities, and 5 = death.

In the event of an AE rated ≥2 the Clinical Director will instruct the subject to obtain medical treatment from a qualified healthcare professional. If the subject becomes ill or is physically injured due to the use of the Elitone™ device, she will not be responsible for the costs required to diagnose or treat such injury. The costs of diagnosis and medical care for any complication, injury, or illness caused by the study device or properly performed non-standard of care investigational procedure required by the study will be covered by Elidah, as long as the subject has followed the study protocol. The subject will not lose any of her legal rights and she does not release Elidah and the study staff from liability for mistakes or intentional misconduct by participating in the study.

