## 8. INTERVENTION DISCONTINUATION

Subjects in the study have the right to discontinue treatment at any point during the study and for any reason. If the subject chooses to discontinue, a reason for discontinuation will be recorded and every effort will be made for the subject to complete the post-study activities defined in Table 5-1.

Elidah may wish to discontinue intervention for a subject for a variety of reasons including those listed below. Effort will be made to bring the subject into study compliance prior to terminating participation.

- Purposeful improper use of the device
- Failure to treat per the assigned schedule
- A recurring adverse event or unanticipated problem.
- Failure to maintain the Daily Log for greater than 2 weeks

A pause on enrollment and/or treatment of active subjects may occur if Elidah discovers a serious issue with the device/treatment (see 7.3). Elidah maintains the right to discontinue the study at any point and for any reason. Stopping treatment does not pose any risk to subjects. The study may be discontinued at any time by the IRB, FDA, or other regulatory or government agency as part of their duties to ensure that research participants are protected.

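### The protocol describes no scheduled, standard adverse event inquiry, and the default hardcopy log is seen only at study end, so events that subjects do not report themselves may be missed or seen late

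*Combined protocol and SAP*

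**What the plan says.** **Role of adverse events.** Section 2.2 sets the safety part of the primary endpoint: "Safety is determined by review of Adverse Events as defined in 7.3, and determination of no serious adverse event during the study". Sections 5.3 and 7.3 also treat adverse events as the main safety measure. Table 5-1 marks them for each treatment week and again post-study.

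**Routes of detection.** The adverse event entry in 5.3 only refers to 7.3, which says: "Adverse events may be identified through direct communication with the subjects and through analysis of study materials". Section 7.4 gives the active route: "Subjects are instructed to report adverse events at the time of occurrence via either phone or email". It then adds: "Adverse events may also be identified during routine communication with the subject", with the sixth-week follow-up as its example, and names Daily Log review as a further possibility.

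**The contacts.** Section 4.5 schedules contacts after weeks 1, 6 and 12. Their stated purpose is "to confirm ongoing participation and to provide the opportunity for subjects to ask questions".

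**The log.** Section 5.3 says: "The log is maintained by the patient in hardcopy and returned to Elidah at the end of the study for analysis". An equivalent electronic form is allowed as an alternative. The fields named are treatment completion, intensity, episodes, pads and free notes, and the list is introduced as partial.

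**Rules that need sight of the log.** Section 8 gives grounds on which the sponsor may discontinue a subject. One is "Failure to maintain the Daily Log for greater than 2 weeks"; another is failure to treat on schedule.

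**The concern.** Treatment is self-administered at home and no visits are described, so the routes above carry all of the safety monitoring. Table 5-1 suggests weekly collection, but nothing in the text produces a weekly adverse event record. Section 7.2 expects skin irritation and muscle fatigue, which some subjects may not think worth a call.

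A missed event makes the device look safer. If capture depends on what each subject chooses to report, the safety summary partly reflects how events were elicited. There is also an internal mismatch. Section 7.4 counts log review as a detection route and section 8 uses log lapses as a ground for action, but under the default in 5.3 the treatment-week log is not in the sponsor's hands until treatment is over.

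**Working it through.** The plan states no adverse event rate, capture rate or safety sample size, so there is no figure of its own to reproduce. The check compares the routes and then works out the timing.

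**1. Each route against what Table 5-1 implies**

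| Route | Initiated by | Adverse event question described? | When the sponsor sees it |
|---|---|---|---|
| Phone or email (7.4) | Subject | No; a standing instruction | At occurrence, if reported |
| Contacts (4.5, 7.4) | Sponsor | No | After weeks 1, 6 and 12 |
| Hardcopy log (5.3) | Subject | None among the fields named | End of study |
| Electronic log (5.3) | Subject | None among the fields named | No transmission or review interval stated |
| Post-study survey (6.6) | Sponsor | Sensation and contraction only | End of study |

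The optional app in 4.5 tracks intensity, days used and leaks, and does not replace the diary. No route is a scheduled, standard adverse event inquiry.

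**2. Exposure between contacts (Table 5-1)**

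- Total sessions: 6×5 + 3×3 + 3×1 = 42.
- Weeks 2-6, between the first and second contacts: 5×5 = 25, and 25/42 = 59.5%.
- Weeks 7-12, between the second and third contacts: 9 + 3 = 12.

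**3. Waiting time for an event that is not self-reported**

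Assume that events fall evenly over 12 weeks, that contacts take place at the ends of weeks 1, 6 and 12, and that the event does come up at the next contact.

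- Mean wait: (1×0.5 + 5×2.5 + 6×3)/12 = 31/12 = 2.6 weeks; maximum 6 weeks.
- Share waiting more than 2 weeks: (0 + 3 + 4)/12 = 58%.
- If the event is visible only in the hardcopy log: mean 12/2 = 6 weeks and maximum about 12 (13 with the extension week), plus the 3 days that 5.4 requests for return.

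An event at the end of week 2 would wait about 4 weeks for the week 6 contact, or about 10 weeks if it is seen only in the log. A self-reported event has essentially no planned delay.

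**4. Logs that may not come back**

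Sections 5.2 and 9.1 allow for 70-80 enrolled to obtain 60: 10/70 = 14% to 20/80 = 25%. Section 5.2 ties this allowance to subjects who do not complete treatment and return materials. Their hardcopy logs may never arrive.

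**5. What incomplete capture would do (illustration only)**

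With no events of a given type recorded in 40 active subjects, the one-sided 95% upper bound is 1 − 0.05^(1/40) = 7.2%. If only a fraction c of true events is captured, the bound on the true rate is 7.2%/c. For a true rate of 5%, the chance of recording at least one event is 1 − (1 − 0.05c)^40.

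| c (assumed) | Upper bound | Chance of at least one record |
|---|---|---|
| 100% | 7.2% | 87% |
| 75% | 9.6% | 78% |
| 50% | 14.4% | 64% |

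The values of c are assumptions and nothing in the documents supports any one of them. Capture is likely to be better for serious events than for mild ones.

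**The case against.** The case on the other side is substantial.

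- **Subjects are told to report at occurrence.** The instruction in 7.4 covers timing as well as route. A reader might infer that the in-study safety rules cannot act in time. The documents do not support that: a reported event can at once trigger the halt in 9.4, the grade 2 or higher actions in 7.4 and 7.5, and the recurring-event ground in section 8. This stands.
- **The week 6 contact is named in 7.4 as a detection route.** The purpose given in 4.5 is a retention purpose, and the two sections should be read together. This stands, but the wording is permissive and neither section describes a question.
- **The forms are not in view.** The field list in 5.3 is expressly partial. The Daily Log, post-study questionnaire, Adverse Event Log and subject instructions are separate documents and may contain prompts. This stands, so the point concerns what the protocol describes. If prompts exist, the protocol should cite them.
- **There are other sources.** Section 7.3 includes study materials generally, 6.6 asks about sensation, and section 8 records reasons for discontinuation. A reader therefore cannot say that events are found only by self-report, contacts or the log. None of these sources is a described adverse event inquiry.
- **The log-lapse and missed-session grounds concern compliance and are discretionary.** This stands. Their failure for hardcopy subjects is an operational mismatch and does not show that safety rules break down.
- **Section 10.5 justifies light monitoring by low risk.** That supports having no extra visits. It is not a reason to leave the question out of contacts that already take place.

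A reader might also infer that the safety endpoint is under-counted, or attach a percentage to the shortfall. Any such percentage only restates an assumed capture rate. The documents show a risk of unknown size.

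**Conclusion.** The point holds as a gap in ascertainment and timing. The protocol describes no scheduled, standard inquiry behind the weekly adverse event marks in Table 5-1. Mild and moderate events that subjects do not volunteer may go unrecorded or be learned of late. For hardcopy subjects, log review and the lapse ground in section 8 cannot operate during treatment, and missed sessions are not visible from the log until it is returned.

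The firm figures are the 5-week and 6-week gaps between contacts and the 60% of prescribed sessions that fall in the first gap. They measure exposure without a scheduled contact, not events missed. The waiting times rest on evenly spread events, and the size of any under-ascertainment is unknown. The conclusion also assumes that the separate forms do not already contain an adverse event prompt. The change is cheap relative to the role of safety in the primary endpoint, so it should be made.

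**What to change.** - At the existing week 1, 6 and 12 contacts, ask one scripted adverse event question, identical in both arms. The staff who speak with subjects are already blinded under 9.3. Record the answer, including a negative one, on the Adverse Event Log (FORM-9).
- Add a yes/no item on any new or worse symptom to the Daily Log (FORM-3) and the post-study questionnaire (FORM-4), unless they already have one.
- Have subjects send log pages to date, by photo or electronic form, at the week 1 and week 6 contacts. Section 5.4 already has them submit the baseline week's log data before treatment, so the step is familiar.
- Reconcile 5.3, 7.4, section 8 and Table 5-1, so that the stated collection schedule and the log-based grounds match when the log is actually seen.

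**Cost.** One question at three existing contacts, at most one item on each of two forms, and log pages sent twice. No new visits or staff. Subjects do slightly more and more minor events will be recorded. Answers may occasionally hint at the assigned device, a risk that 9.3 already recognises and documents.
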